## Tool Revision History

Version Number 1.1

Version Date 10/30/13

Summary of Revisions Made:

- 1) Clarified determination of adverse event severity with reference to neonatal toxicity tables (Appendix D) and additional guideline for assessing laboratory values (Appendix E) (see section 7.4.1).

Version Number 2.0

Version Date 6/30/2018

Summary of Revisions Made:

- 1) Changes in IND personnel. [name] will assume responsibilities as the sponsor-investigator (see letters from Drs. [name] and [name]). New study personnel have been added.
- 2) Changed the number and timing of visits. Since the differentiation between preterm infants with normal intestinal barrier maturation and those with delayed maturation was significant at the second timepoint (Study d8) or approximately 7-10 days of age, we will limit the dual sugar solution administration to one administration per subject between d7 and 10 of postnatal age.
- 3) Eliminate blood draws for zonulin measurement. There was no association of serum zonulin and the gold standard urinary Lactulose/Rhamnose ratio in the initial cohort of 43 subjects, so no further blood draws will be done.
- 4) Safety Monitoring: The U. Maryland IRB has approved the change from a DSMB to a single safety monitor.
- 5) Stool microbiome: Addition of stool microbiome analysis in relation to intestinal permeability measured by La/Rh ratio.

Version Number 2.1

Version Date 8/6/2019

Summary of Revisions Made:

- 1) Increase the sample size: Sample size will be increased to total 200 based on sample size calculation. A total of 200 sample size was calculated to obtain high precision in correlations between features of the stool microbiota and intestinal permeability (IP). Since 83% subjects in the first cohort had high IP ( $La/Rh \geq 0.05$ ) at study day 8, a sample size of 166-236 provides marginal error of 0.05 (maximum sampling error of 5%) and alpha of 0.05 (95% confidence level) to detect correlations between features of the microbiota and changes in IP and to achieve an expected sensitivity of 0.8-0.9 and expected specificity at 0.9-0.95.

- 2) Change in stool collection frequency: Instead of collecting stools twice per day from enrollment until postnatal d21, stools will be collected twice per day from enrollment until postnatal d14 and once on postnatal d21. The rationale for this change is to concentrate stool collections around day of IP measurement by urinary La/Rh ratio to analyze the correlations of stool microbiota composition and IP.
- 3) Delete site Mercy Medical Center: Due to limited study personnel and adequate enrollment at main site University of Maryland Medical Center, Mercy Medical Center will be dropped as an active site. Enrollment will continue at University of Maryland Medical Center.

### List of Abbreviations

AE	Adverse Event/Adverse Experience
A1AT	Alpha 1 antitrypsin
CFR	Code of Federal Regulations
CIOMS	Council for International Organizations of Medical Sciences
CLIA	Clinical Laboratory Improvement Amendments
CONSORT	Consolidated Standards of Reporting Trials
CRF	Case Report Form
DCC	Data Coordinating Center
DHHS	Department of Health and Human Services
DSMB	Data and Safety Monitoring Board
FDA	Food and Drug Administration
FDAAA	Food and Drug Administration Amendments Act
FIH	First in Human
FWA	Federalwide Assurance
GCP	Good Clinical Practice
HIPAA	Health Insurance Portability and Accountability Act
IATA	International Air Transport Association
ICF	Informed Consent Form
ICH	International Conference on Harmonisation
ICMJE	International Committee of Medical Journal Editors
IND	Investigational New Drug
IoR	Investigator of Record
IRB	Institutional Review Board
ISM	Independent Safety Monitor
La/Rh	Lactulose Rhamnose Test
LAR	Legally Authorized Representative
MedDRA*	Medical Dictionary for Regulatory Activities
MOP	Manual of Procedures
N	Number (typically refers to subjects)
NCCAM	National Institute of Complementary and Alternative Medicine
NDA	New Drug Application
NG	Naso-gastric
NICU	Neonatal Intensive Care Unit
NIH	National Institutes of Health

NLM	National Library of Medicine
OCRA	Office of Clinical Research Affairs, NIH, DHHS
OG	Oro-gastric
OHRP	Office for Human Research Protections, DHHS
OHSR	Office for Human Subjects Research, NIH, DHHS
ORA	Office of Regulatory Affairs, NIH, DHHS
PHI	Protected Health Information
PI	Principal Investigator
QA	Quality Assurance
QC	Quality Control
SAE	Serious Adverse Event/Serious Adverse Experience
QM	Quality Management
SMC	Safety Monitoring Committee
SOP	Standard Operating Procedure
US	United States
WHO	World Health Organization

### Protocol Summary

Measures of Intestinal Permeability in Preterm Neonates

**Title:**

**Abbreviated Title**

Intestinal Permeability in Preterm Neonates

**Phase:**

1

**Population:**

A sample of N= 200 inpatient neonates between 24-32 week gestational age. *No gender or ethnic exclusions apply.*

**Number of Sites:**

1

**Study Duration:**

24 months

**Subject Participation**

28 days

**Duration:**

**Agent or Intervention:**

Lactulose/rhamnose ratio measurement of intestinal permeability in preterm neonates.

[figure not shown]
**Objectives:**

To assess intestinal permeability in preterm infants with the lactulose/rhamnose ratio in urine and relationship to stool microbiome characteristics

**Endpoints:**

Onetime measurement of *in vivo* permeability determined by the urine La/Rh ratio between 7-10 days of age and serial stool microbiome changes between postnatal d5-d14 and at PND21 in a cohort of preterm neonates. The goal is to determine the changes in the intestinal microbiome characteristics in association with impaired intestinal barrier function (La/Rh  $\geq 0.05$ ) at 7-10 days in preterm neonates.

## 2 BACKGROUND INFORMATION AND SCIENTIFIC RATIONALE

### 2.1 Background Information

*Intestinal barrier:* The human intestine is lined by a single layer of cells exquisitely responsive to multiple stimuli, and is populated by a complex climax community of microbial partners. Under normal circumstances, these intestinal cells form a tight, but selective barrier to “friends and foes”: microbes and most environmental substances are held at bay, but nutrients are absorbed efficiently (1, 2). Environmental antigen(s) that gain access to the intestinal submucosa via paracellular passage from the intestinal lumen across an aberrant mucosal barrier trigger a host inflammatory response. There may be genetic variation in susceptibility to recognize, and potentially misinterpret, these non-self antigens (1). In all cases, increased permeability precedes disease and causes an abnormality in antigen delivery that triggers the multi-organ process leading to the inflammatory response (1).

*Measurement of Intestinal Permeability:* The measurement of the urinary excretion of orally administered isotonic solution of non-metabolized sugar probes have been used extensively for 30 years to assess intestinal permeability in health and disease in adults (3-9) and in preterm (10-13) and term infants (13-15) as well as older children. Lactulose, a disaccharide is a constituent of infant formulas (10) and is safe treatment for constipation (16) at doses 8-15 times higher than used in the assessment of intestinal permeability. L-Rhamnose is a naturally occurring monosaccharide without known biologic effects. It is found in the polysaccharides of gums, cardiac glycosides, and foods such as oranges, French beans, winter cabbage, and carrots (17) and is used in food flavoring (10). It is not absorbed by the human small intestine and reaches the colon where fermentation may produce propionate. The percent urinary excretion of orally administered lactulose and rhamnose are markers of the intestinal paracellular and transcellular pathways, respectively. The sugar probe tests have been used to safely estimate intestinal permeability in pediatric conditions including celiac disease (18), atopic eczema (19, 20), cystic fibrosis (21, 22), major burns (23) and diarrhea (24-26). The sugar probe has also been safely used to assess intestinal permeability in ill newborns with birth asphyxia (10), necrotizing enterocolitis (NEC) (11) and congenital heart disease (15, 27). A recent review confirmed that the use of the sugar absorption tests have been found to be safe in newborns (28). We have summarized the literature of the use of lactulose and L-rhamnose as sugar probes in studies of preterm and term infants (Table 1) and older infants and children (Table 2) (see IND section 6.2).

*Intestinal functions and prematurity:* Epithelial barrier integrity is itself dynamic and matures over time starting soon after birth, though the mechanisms regulating dynamic permeability are poorly understood. Low birth weight, prematurity, and early postnatal age are associated with a leaky gut (34). Although intestinal permeability (IP) is higher at birth in preterms than term infants, there is usually rapid maturation of the intestinal barrier over the first few days of life in both populations (34). Diet also affects intestinal permeability with breast milk feeding lowering

IP more rapidly in the first month of life compared with cow milk-based formula in term (35) and in preterm neonates (36).

[figure not shown]
***NEC and its pathogenesis:*** NEC, a life-threatening, GI emergency characterized by increased IP, affects approximately 7 to 10% of preterm neonates, and typically occurs within 7 to 14 days of birth (37, 38) with mortality as high as 30-50% (39). NEC symptoms mainly involve GI dysfunction, such as abdominal distension and feeding intolerance, but the presentation can be non-specific with few warning signs. Current therapies may be invasive, including surgical interventions that are often ineffective due to the rapid progression of the disease. Prematurity is the greatest risk factor for development of NEC (40, 41), due to physiological immaturity of the GI tract and altered levels of the normal GI microbiota. Several studies suggest that the initiation of an intense systemic and local inflammatory cascade leads to intestinal necrosis (42-47). Antenatal exposure to infection/inflammation may predispose the developing intestinal mucosa to subsequent injury or dysregulated inflammatory responses. Previous studies have linked presence of amniotic fluid infection/elevated cytokines, (48) cord blood cytokines, (49, 50) and umbilical cord inflammation (51) with risk for NEC in preterm neonates. In a rat model of NEC, maternal prenatal exposure to microbial LPS led to increased frequency and severity of intestinal injury (52). Taken together, these observations suggest that intestinal injury may be initiated *in utero* and contributes to increased IP at birth in the preterm neonate. Many of the defense mechanisms present in the mature intestine, such as peristalsis and tight junctions between intestinal epithelial cells (37) are decreased in an immature intestine, and thus bacteria normally confined to the intestinal lumen are able to reach systemic organs and tissues. Bacterial translocation triggers the activation of an exaggerated inflammatory response, which leads to further epithelial damage.

## **2.2 Scientific Rationale**

Despite improvements in neonatal intensive care, the birth weight-specific incidence of NEC has not changed over the past 2 decades. However, the total burden of disease is increasing due to increased survival of very immature infants. Mortality remains high and survivors experience significant morbidity including post-surgical short bowel syndrome and its consequences (prolonged dependence on total parenteral nutrition, recurrent infections, poor growth, and liver failure), prolonged hospitalization, and long-term neurodevelopmental impairments. Intestinal barrier immaturity is the proximate cause of susceptibility to NEC in preterm neonates. Although intestinal permeability is higher at birth in preterm compared to term infants (34), *in utero* infection/inflammation and post-natal acquisition of pathogenic bacteria may further exacerbate intestinal injury (48-53). Despite intensive efforts, no clinical factor or routine laboratory test alone or in combination has been described that predicts the 7-10% preterm neonates at-risk for this potentially life-threatening complication (54). Although increased intestinal permeability is a major risk factor for NEC and *in vivo* intestinal permeability has been assessed in infants with the urine LA/MA ratio or urine La/Rh ratio, few preterm infants <30 wk gestation have been included in the prior studies of intestinal permeability.

Since current therapies for NEC may be invasive, including surgical interventions that are often ineffective due to the rapid progression of the disease, there has been considerable focus on developing preventive therapies. Probiotic therapy is a promising, low-cost, and likely safe intervention to reduce intestinal permeability in at-risk infants. There have been at least 11 RCTs and a recent meta-analysis of probiotic supplementation to prevent NEC in preterm neonates (55). Although there was a 30% reduction in NEC incidence in these trials, various formulations, doses, and duration of therapy were used, infants <1000 g BW with the highest NEC incidence were under-represented, and no FDA-approved products are available to assure quality and safety under good manufacturing practices. In preparation for future trials of the efficacy of probiotics to prevent NEC in preterm infants, the proposed observational study will utilize the La/Rh ratio to determine in vivo intestinal permeability in infants 24-32 weeks gestation during the 2 weeks of life.

### 2.3 Preliminary Data

[figure not shown]

**Figure 1.** Microbial community diversity and intestinal permeability at study time points day 1, 8, and 15 for a cohort of 43 preterm infants (<33 weeks gestational age). Microbial community diversity is calculated as OTU richness based on 16S rRNA gene amplicon high-throughput sequencing. Intestinal permeability was calculated as the ratio of non-metabolized sugar probes

gestational age (<31.7wk) were identified to be the most discriminatory features for elevated IP by supervised learning scheme, reaching an accuracy of 86.1%. (5) *Clostridiales* and *Bifidobacteriales* are the most abundant bacteria groups in later stages (phase II/III at 6-18

Our analysis of the initial cohort of 43 preterm infants recruited for the IND protocol, and others' previous studies have shown that IP is high at birth in preterms (<33wk gestation) with a rapid maturation of the intestinal barrier over the first 2 weeks. However, in some infants, high IP persisted and/or recurred in association with altered levels of the normal microbiota (bacteria community composition). Specifically, we observed that (1) rapid maturation of intestinal barrier function, characterized by decreased IP, correlates with increased microbial community diversity (Figure 1), and most outstandingly, the increased abundance of beneficial bacteria *Clostridiales* (Figure 2); (2) *Clostridiales* is highly transcriptionally active and co-active with the probiotic bacterium *Bifidobacterium*; (3) neonatal factors, including early introduction of breast milk, shorter period of antibiotic exposure, and later gestational age, favor the early colonization of the gut microbiota by members of *Clostridiales* and *Bifidobacterium*, which altogether are associated with improved intestinal barrier in preterm infants; (4) low *Clostridiales* spp. abundance (<5%) and early

months of age) as shown in Figure 2, suggesting a process of gaining prosperity of these two bacterial groups during intestine development after birth. Altogether our preliminary results suggest the early colonization of the natural occurring probiotics strains *Clostridiales* and *Bifidobacterium* strongly associate with rapid maturation of intestinal barrier function, and their measurement are highly promising for early detection and as potential nutritional supplement to prevent NEC in the high-risk preterm population.

We propose in this study to recruit additional 157 preterm subjects and to combine with our existing 43 preterm subjects to form a statistically powered cohort at 200 (justified in study size analysis in research design), to address our hypothesis that the two naturally occurring beneficial bacteria *Clostridiales* and *Bifidobacterium* are rapidly gaining prosperity during normal intestine development in association with improved barrier function measured by La/Rh ratio. Overall, this continuation of the initial study builds on the previous findings that identified commensal bacteria *Clostridiales* and *Bifidobacterium* species as a strong indicator to the lowered IP and rapid maturation of intestinal barrier, to substantiate measurement of these probiotic strains combined with associated neonatal factors to form an accurate, rapid detection of intestinal permeability abnormality.

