**Secondary Objectives:**

- 1) To assess stool microbiome characteristics in association with intestinal permeability in preterm infants measured by the urinary lactulose/rhamnose ratio

- 2) *To analyze the correlation of stool calprotectin, sIgA, and lactoferrin to urinary lactulose/rhamnose ratio and stool microbiome characteristics in neonates born between 24 and 32 weeks of gestational age.*

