#### Postnatal d7-10

- ∞ In vivo IP will be determined by means of the urine La/Rh test. Briefly, preterm neonates will be administered a 1 mL/kg La/Rh solution (8.6 g of lactulose + 140 mg of rhamnose/100 mL) via a clinically indicated OG or NG tube. The La/Rh solution will be prepared by the Investigational Drug Pharmacy (IDS) and administered by gavage. Starting at the time of the dose of the La/Rh solution, urine will be collected for a 4-hour period with cotton balls. If a participant does not require an OG/NG tube the solution will be administered orally by nippling.
- ∞ Continue collecting available stool samples daily until PND14 and single sample on PND21 for microbiome, calprotectin, sIgA, and lactoferrin analysis. Record daily weight, and weekly height, and head circumference.

- ∞ Demographic and clinical data will be collected from the chart.
- ∞ Collect adverse events from medical chart.

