#### **6.9 Product Administration (include allowable time windows)**

Each enrolled preterm neonates will be administered a 1 mL/kg La/Rh solution (8.6 g of lactulose + 140 mg of rhamnose/100 mL) via a clinically indicated OG or NG tube once between 7-10 d of age. The La/Rh solution will be administered by gavage with an enteral feed. Total volume of La/Rh ingested will be recorded. Urine will be collected for a 4-hour period *with cotton balls*. Total volume of urine during the 4 hour collection will be recorded. The urine will be aliquoted and 4 ml of urine saved for analysis. Nursing staff in the NICU will be trained in the procedures prior to study initiation. Only trained NICU staff will be allowed to be responsible for administering the La/Rh solution and collecting the urine. A minimum of 2 ml of urine will be collected. If urine leaks around the cotton balls, then the diaper will be weighed and the diaper weight will be used to estimate the urine volume for the 4 hour collection period. If less than 2 ml urine is collected, then the test will be repeated on another day within the 7-10d window by

administering 1 ml/kg La/Rh solution (8.6g of lactulose + 140 mg of rhamnose/100mL) via an OG/NG tube followed by a 4 hour urine collection. The urine will be stored at -80°C until processed. The sugars will then be measured in urine by HPLC.

Urine La and Rh will be measured in the lab of our collaborator [name] from the University of Calgary, Canada.

*Stool calprotectin, sIgA, and lactoferrin will be measured by commercial ELISA kits.*

Rescue Therapy- NA

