gestational age (GA) at 24-32 weeks, information including extensive data on demographics, obstetric and neonatal factors, medication exposures, and feeding practices will be obtained. Fecal specimen will be collected to generate bacterial community composition and structure using high-throughput sequencing of 16S rRNA gene amplicon and to calculate bacterial total copy number using quantitative PCR. Urine specimen will be used to measure the non-metabolized sugar lactulose (La) and rhmnose (Rh) concentration using high-pressure liquid chromatography (HPLC), and their ratio will be used to calculate high IP ( $La/Rh > 0.05$ ) and low IP ( $La/Rh \leq 0.05$ ). (2) Discriminatory classifier generation. The bacterial abundance and neonatal information will be used to form the data matrix and the high or low IP category will be used to “label” a sample as its class, which is used in supervised machine learning scheme with cross-validation (construct model on a sample set and evaluate on a different sample set to avoid over-prediction) to direct generating the classifier after data preprocessing and evaluation. The most discriminatory features (i.e. bacterial species and/or neonatal factors) will be characterized by its contribution to identify a sample in a high or low IP class. (3) We will evaluate the contribution of each discriminatory feature to IP classification using permutation importance measurement (5).

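### The 43 infants who generated the Clostridiales/Bifidobacterium hypothesis are pooled with the 157 new infants meant to support it, and no result is planned in the 157 alone

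*Combined protocol and SAP*

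**What the plan says.** Section 2.3 (Preliminary Data) describes an initial cohort of 43 preterm infants. In them, lower permeability went with more Clostridiales, which was co-active with Bifidobacterium. Clostridiales below 5% and gestational age below 31.7 weeks are named among "the most discriminatory features for elevated IP by supervised learning scheme, reaching an accuracy of 86.1" per cent. The same section then plans to "recruit additional 157 preterm subjects and to combine with our existing 43 preterm subjects to form a statistically powered cohort at 200". The enlarged cohort is to address the hypothesis about these two bacterial groups, and to substantiate their measurement as a rapid means of detecting abnormal permeability.

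The matching objective is secondary objective 1 in section 2.5: "To assess stool microbiome characteristics in association with intestinal permeability in preterm infants". In section 10.6, the correlations and ROC curves concern calprotectin, sIgA and lactoferrin. The only analysis there that relates the microbiome to La/Rh is the classifier: "The bacterial abundance and neonatal information will be used to form the data matrix", each sample is labelled high or low permeability, and cross-validation is used to "construct model on a sample set and evaluate on a different sample set to avoid over-prediction". Nothing in 10.6 separates the 157 from the 43 or names the 43 as a training set.

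On sampling, the Protocol Summary makes "serial stool microbiome changes between postnatal d5-d14 and at PND21 in a cohort of preterm neonates" an endpoint, and section 6.4 says "Continue collecting available stool samples daily until PND14 and single sample on PND21". The sugar test is given "via a clinically indicated OG or NG tube once between 7-10 d of age" (section 6.9).

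**The concern.** Data that suggested a hypothesis cannot also confirm it independently. If the Clostridiales signal, or the choice of cut-offs, owes something to chance in the 43, that chance component is carried into any estimate made in the 200. The plan provides no result beside it that would show this. Section 2.3 presents the extension as support for what was seen in the 43 infants and as a step towards a detection tool, so a reader will take the n = 200 result as confirmation. What is at stake is the evidential weight of secondary objective 1, not the primary estimates of the La/Rh distribution.

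A second, smaller matter is the cross-validation unit. Section 10.6 labels and splits samples without saying whether a sample is an infant or a stool. A new infant can contribute several stools but has a single La/Rh label. If several stools per infant entered the matrix and folds were formed by stool, the same infant could sit in both the training and the test set.

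**Working it through.** **Inputs.** 43 existing, 157 new and 200 in total (section 2.3); 83% high permeability at study day 8 in the first cohort, margin 0.05, 95% confidence, N range 166-236, expected sensitivity 0.8-0.9 and specificity 0.9-0.95 (Sample Size Considerations, section 10).

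**The plan's own figures.** 43 + 157 = 200 is right. The lower end of the range reproduces as a sensitivity calculation: 1.96² × 0.9 × 0.1 / 0.05² = 138.3 high-permeability infants, and 138.3 / 0.83 = 166.6 subjects. The upper end reproduces at sensitivity 0.85 (195.9 / 0.83 = 236.0), not at the stated 0.80 (245.9 / 0.83 = 296.2). The range therefore speaks to sensitivity only. The same formula for specificity 0.95 and 0.90 gives 429 and 813. That mismatch is a separate issue; it matters here only for judging the cost of a 157-only result.

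**Share of the cohort.** 43/200 = 0.215.

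**Illustration of non-independence.** Suppose a feature has no true association and was kept because Z₁ > 1.96 in the 43. With Z₂ the independent statistic in the 157:

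- Z_pooled = √(43/200) Z₁ + √(157/200) Z₂ = 0.464 Z₁ + 0.886 Z₂.
- If Z₁ is exactly 1.96, Z₂ must exceed (1.96 − 0.464 × 1.96) / 0.886 = 1.19, which has probability 0.118.
- Averaged over all Z₁ > 1.96, P(Z_pooled > 1.96 | Z₁ > 1.96) = 0.165. With a threshold of 2.576 in the 43 it is 0.245.
- In the 157 alone, P(Z₂ > 1.96) = 0.025 in either case.

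If instead the feature was the best of 10, 20 or 50 independent null features in the 43, the pooled two-sided error is 11.8%, 14.8% or 19.0%, against 5% in the 157. The thresholds and feature counts are assumptions; the documents give neither.

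**Precision in the 157.** At 83% prevalence there are about 130 high- and 27 low-permeability infants in the 157, and 166 and 34 in the 200. The half-width is 1.96 × √(p(1−p)/n).

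| | 157 alone | pooled 200 |
|---|---|---|
| Sensitivity 0.9 | 5.2 points | 4.6 points |
| Specificity 0.9 | 11.3 points | 10.1 points |
| 95% CI for r = 0.3 (Fisher z) | 0.15 to 0.44 | 0.17 to 0.42 |

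**Fold unit.** Daily stools from day 5 to day 14 plus day 21 give up to 10 + 1 = 11 per new infant, if available, against one label. A null simulation (200 infants, 83% high, 10 stools each, 20 features, 3-nearest-neighbour, 5 folds, within-infant correlation 0.3, 0.5 and 0.7) gave accuracy 0.80, 0.87 and 0.98 with folds by stool, and 0.76-0.78 with folds by infant. All settings except 200 and 83% are assumed. Under other assumed settings (11 stools, correlation 0.3-0.5) a linear discriminant showed no inflation of accuracy. This shows a possible direction and gives no size for this study.

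**The case against.** The strongest reply is that pooling is declared openly, the study is observational, and secondary objective 1 asks only to assess an association. No section claims independent validation. Section 10.6 plans a newly built classifier with cross-validation, not a retest of the old rule, and no significance test of any taxon. Much of this stands. The 16.5% figure describes a test that 10.6 does not contain, so it can only illustrate. What does not stand is the suggestion that cross-validation settles the matter: it guards against overfitting within the 200 but does not make the 43 new evidence on a hypothesis they produced.

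A reader might infer that pooled accuracy will be overstated by a calculable amount, by giving the reported 86.1% a weight of 21.5%. The documents do not support this. They give no denominator, time point or validation method for 86.1%; 37/43 is 86.0%, while 31/36 is 86.1%, so it is not plainly a count over the 43 infants. Nor does 10.6 plan to score the old rule in all 200.

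A reader might also infer that the planned cross-validation leaks between folds. That is not shown either. Collecting serial stools does not mean that all of them enter the matrix, the sample size is counted in subjects, and the stated intent is to evaluate on different samples. The gap is one of wording.

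Finally, 157 falls below the plan's own 166-236. That is true and has to be stated with the 157-only result.

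**Conclusion.** The concern holds in a limited form. The hypothesis and the discriminatory features came from 43 infants who make up 21.5% of the cohort that is to substantiate them, and no result is planned in the 157 who could test them independently. The n = 200 result should therefore not be read as independent confirmation. The 16.5% against 2.5% contrast shows the kind of distortion possible, assuming a null feature selected at z > 1.96 in the 43 and a pooled test that the plan does not specify. Pooling does not in itself inflate the cross-validated accuracy of the new classifier, and the primary objective is untouched. That the classifier is fitted on all 200 is inferred from section 2.3 and the sample size text; 10.6 does not say so outright. The half-widths assume that 83% high permeability carries over to the new infants and that all 157 have a usable La/Rh result. The fold-unit point is a conditional clarification: with one stool per infant, stool-level leakage does not arise.

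**What to change.** Add to section 10.6:

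1. The Clostridiales/Bifidobacterium association with La/Rh at 7-10 days is reported in the 157 new infants as the independent result, beside the pooled 200.
2. The performance of the first-cohort classifier is reported in the same way. Section 2.3 does not say how its features combine or at which time point they apply, so the sponsor must lock the features, combination rule, cut-offs and time point from the 43 before the new data are analysed.
3. The 157-only result is presented as an estimate with its interval, not as meeting the 5-point margin.
4. The number of stools per infant in the classifier matrix is stated. If it is more than one, folds are formed by infant, with twin pairs kept together (section 4.2 excludes only triplets and higher), and any label-based feature selection is done inside the training folds.

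The cost is analysis-plan wording and minor recoding, with no new data. Intervals in the 157 are somewhat wider, as tabulated, and 157 is below the 166-236 range. The pooled analysis is kept, so no precision is lost there.
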